# E. Description of Population to be Enrolled

#### 1. Target Enrollment

The target accrual is based on the primary endpoint (safety). The safety population is defined as all patients who received at least one dose of the enoxaparin regimen. In order to achieve adequate power and precision for determination of safety in the primary analysis (see also section G, below), the target enrollment is 38 evaluable children, from among a total of 12-15 participating sites. Participants who do not received at least one dose of the enoxaparin regimen (i.e. early termination, withdrawal of consent) will be replaced. Anticipating an 85% retention rate, we will enroll up to 45 participants. Both males and females of all races and ethnic groups are eligible for this study.

Table 1. Schedule of Assessments.

Assessment	Screening (Within 72 hours of hospital admission)	Enrollm ent Day 0	Day 1	Day 2	Day 3 *	Day 7 *	Day 14 *	Day 30 (+/- 2 days)
Informed consent		Х						
Enrollment		Х						
Full H&P	Х							
Focused H&P			Х	Х	Х	Х	Х	
Weight	Х							
CBC with platelet count	Х				Х	Х	Х	
PT and aPTT 	Х				Х	Х	Х	
Fibrinogen 	Х				Х	Х	Х	
Serum creatinine	Х				Х	Х	Х	
Urine pregnancy screen 	Х							
Research blood specimen 		Х	Х	Х	Х	Х	Х	
Anti-factor Xa level 			Х	+/- X				
SAE Monitoring			Х	Х	Х	Х	Х	Х
Bleeding event (based on focused interim H&P)			Х	Х	Х	Х	Х	Х
VTE event (based on focused interim H&P, with radiological confirmation when suspected clinically)			х	х	х	х	х	х
Telephone visit 								Х

Obtained for research purposes if not already being obtained clinically.

 For participants <20kg: (1) 3ml blue top tube and (1) 4mL CPT Tube (7mL total). For participants  $\ge$ 20kg, (1) 3mL blue top tube and (2) 4mL CPT tubes (11mL total). Research blood collection is for central research lab testing of D-dimer, Clot Formation and Lysis (CloFAL) assay, IL-6, and anti-SARS-CoV-2 IgG, as well as banking plasma, DNA isolated from the buffy coat, and peripheral blood mononuclear cells (PBMCs) for future research.

 Obtained at 4 hours after 1st or 2nd dose of enoxaparin, at initial dosage (mg/kg) and any subsequent change in dosage.

Focused, scripted assessment of symptoms of potential concern for bleeding events, VTE events, and SAEs. Refer to Manual of Operations.

\* If still hospitalized.

Abbreviations: H&P, history and physical exam; CBC, complete blood count; PT, prothrombin time; aPTT, partial thromboplastin time; SAE, serious adverse events; VTE, venous thromboembolism; CT, computed tomography.

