# IV. RESEARCH METHODS: SUMMARY OF STUDY RATIONALE

# A. Primary Outcome

PRIMARY SAFETY: Occurrence of clinically-relevant (i.e., major plus clinically relevant non-major [CRNM]) bleeding within 30 days.

Based upon International Society on Thrombosis and Haemostasis (ISTH) Scientific and Standardization Committee standardized definitions for pediatric trials [12], "Major bleeding" will be characterized by bleeding satisfying any one of the following criteria: 1) fatal; 2) clinically overt and associated with a decrease in hemoglobin of at least 2 g/dL in a 24 hour period; 3) clinically overt and for which blood product is administered; 4) retroperitoneal, pulmonary, or involving the central nervous system; 5) requiring surgical intervention in an operating suite.

"CRNM bleeding" definition includes any bleeding that does not fulfill the above criteria but fulfills one of the following: 1) Bleeding requiring medical or surgical intervention to restore hemostasis; 2) Bleeding for which medical attention is sought.

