#### 2. Inclusion Criteria

#### Inclusion Criteria for COVID-19 Infected Patients:

- 1. Children (birth to <18 years of age)
- 2. Positive nucleic acid test, antigen testing, or antibody testing for SARS-CoV-2 within the past 7 days
- 3. Hospitalized <72 hours post-admission
- 4. One or more signs and/or symptoms of COVID-19 illness within the past 72 hours, as follows:
  - i.) Cough
  - ii.) Fever (oral temperature >100.4°F/38°C)
  - iii.) Chest pain
  - iv.) Shortness of breath
  - v.) Myalgia
  - vi.) Acute unexplained loss of smell or taste
  - vii.) New/increased supplemental oxygen requirement
  - viii.) Acute respiratory failure requiring non-invasive or invasive ventilation
  - ix.) Encephalitis
- 5. Clinical suspicion that the above symptoms are related to COVID-19 infection and not an alternative etiology.

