#### F. Description and Justification of Procedures, Measures, and Data Collection Tools:

There will be minimal laboratory assays, examinations, or other procedures performed solely for the purposes of this study and not currently part of best/standard clinical care.

The first is an additional 11 mL blood specimen (7mL in participants <20kg) obtained at visits on post-enrollment days 1 and 2 (and days 3, 7, and 14 if still hospitalized) for protocol-specified research laboratory investigations (D-dimer, IL-6, anti-SARS-CoV-2 IgG/IgM, and CloFAL assay) and future unspecified research (i.e., banking of plasma, DNA isolated from the buffy coat, and isolated PBMCs). These biospecimens will be stored in the Johns Hopkins All Children's Pediatric Biorepository at the Clinical Coordinating Center. All biospecimen storage tubes are pre-labeled with a unique 2D

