#### Screening/Within 72 hours of hospital admission (Day 0)

- Informed consent
- Enrollment
- Full medical history and physical exam
- Weight
- Initial plasma laboratory evaluation including the following (obtained as research purposes if not already obtained clinically
  - Complete blood cell count with platelet count
  - o PT and aPTT
  - o Fibrinogen
  - Serum creatinine
  - Urine pregnancy screening (beta-HCG)
- Research blood specimen collection

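### A flat 7 mL research draw for every child under 20 kg, from birth, takes about four times as much blood per kg from an assumed 3 kg infant as from a 20 kg child, and the reviewed text sets no limit

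*Protocol*

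**What the plan says.** Protocol Section IV.E.1, Table 1, footnote 2 sets the research blood volume. Below 20 kg it reads "For participants <20kg: (1) 3ml blue top tube and (1) 4mL CPT Tube (7mL total"; from 20 kg it reads "1) 3mL blue top tube and (2) 4mL CPT tubes (11mL total". Both are set volumes, not maxima. Section IV.F repeats them: "The first is an additional 11 mL blood specimen (7mL in participants <20kg) obtained at visits on post-enrollment days 1 and 2", with further draws on Days 3, 7 and 14 for inpatients.

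Table 1 marks the specimen on Days 0, 1, 2, 3, 7 and 14, and the last three carry the condition "If still hospitalized". The Day 0 visit list in Section IV.F also has "Research blood specimen collection". The opening narrative of the same section does not name Day 0.

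The age criterion in Section IV.E.2 is "Children (birth to <18 years of age". The exclusions in Section IV.E.3 contain no minimum weight.

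Under Table 1 footnote 1, PT/aPTT, fibrinogen and anti-Xa are taken for research when they are not already taken clinically. Footnote 3 repeats anti-Xa after each dosage change. Under Minor Protocol Deviations (Section IV.J.4), a missed research specimen counts as a deviation.

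**The concern.** The protocol already accepts that research volume should fall with weight, since it steps down from 11 to 7 mL at 20 kg. But the lowest tier then runs unchanged from a newborn to a child just under 20 kg, so the burden per kg rises steeply as weight falls. These children are assigned an anticoagulant, and the loss is created by the study rather than by their care.

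The text leaves sites little room. The volume is fixed, and leaving out a specimen in a very small infant is recorded as a departure from protocol. Section IV.F describes study-only procedures as few, and the risk discussion in Section IV.K.1 covers bleeding but not sampling loss. What is at stake is avoidable blood loss in the smallest participants, for specimens that serve exploratory assays and future research.

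**Working it through.** **Inputs from the protocol.** Tube volumes are from Table 1 footnote 2. Draw days are from Table 1: three draws by Day 2, four by Day 3, six by Day 14.

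**Assumption.** Infant weight. The documents give none, so a range of 2.5 to 5 kg is shown.

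**Stated figures reproduced.** Below 20 kg: 3 + 4 = 7 mL. From 20 kg: 3 + 2 × 4 = 11 mL. Both match.

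**Reference child.** 11 / 20 = 0.55 mL/kg per draw. Six draws: 66 / 20 = 3.3 mL/kg.

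**Infant of weight w.** Per draw: 7 / w. After n draws: 7n / w. Ratio to the 20 kg child: (7 / w) / 0.55. The number of draws cancels from the ratio.

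| Assumed weight | mL/kg per draw | Days 0-2 (21 mL) | Days 0-3 (28 mL) | To Day 14 (42 mL) | Ratio to 20 kg child |
|---|---|---|---|---|---|
| 2.5 kg | 2.80 | 8.4 | 11.2 | 16.8 | 5.1 |
| 3 kg | 2.33 | 7.0 | 9.3 | 14.0 | 4.2 |
| 3.5 kg | 2.00 | 6.0 | 8.0 | 12.0 | 3.6 |
| 4 kg | 1.75 | 5.25 | 7.0 | 10.5 | 3.2 |
| 5 kg | 1.40 | 4.2 | 5.6 | 8.4 | 2.5 |
| 20 kg (11 mL draw) | 0.55 | 1.65 | 2.2 | 3.3 | 1 |

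The ratio is exactly 4 at 7 / (4 × 0.55) = 3.18 kg. Parity with the 20 kg child is at 7 / 0.55 = 12.7 kg.

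**Choice of reference.** A child just under 20 kg on the 7 mL draw gives 7 / 20 = 0.35 mL/kg. Against that child the ratio at 3 kg is 2.33 / 0.35 = 6.7, so the 20 kg comparison is the milder of the two.

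**If Day 0 is not drawn**, as the Section IV.F narrative reads, there are five draws: 35 mL, or 35 / 3 = 11.7 mL/kg at 3 kg, against 55 / 20 = 2.75 mL/kg at 20 kg. The ratio is unchanged.

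**Not counted.** Coagulation and anti-Xa samples taken for research. Their volumes are not stated.

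**The case against.** Several points on the other side stand.

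- The 14 mL/kg figure is a ceiling. It needs a 3 kg infant still in hospital on Day 14; three draws give half of it.
- The Day 0 draw may precede the first enoxaparin dose.
- No volume limit in the documents is shown to be breached. One may exist in the Manual of Operations or the consent form, neither of which was available, and Section IV.K.1 itself refers to the consent document for risks.
- SAP Section 2.5 reports 38 enrolled, the target number. New wording would help only further enrolment or reuse of the protocol.

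A reader might also infer more than the documents support.

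- **That sampling loss distorts the primary endpoint.** The argument would be that sampling anaemia leads to a transfusion and turns a trivial ooze into a major bleed under "clinically overt and for which blood product is administered". But the endpoint in Section IV.A counts major and clinically relevant non-major bleeding together, and the latter already takes in any bleed that prompts medical attention. Reclassifying such an event would leave the count unchanged. The criterion most naturally means a product given for the bleed itself, and events are centrally adjudicated (Section IV.C). The route is conjecture.
- **That the 4 mL CPT tube serves only banking.** Footnote 2 lists the assays and banked materials for the collection as a whole and assigns none of them to a tube.
- **That Aim 2 seeks out infants.** It names a stratum under one year but sets no quota. The protocol compares age groups only if numbers suffice, and SAP Section 4.1.2 splits baseline data at 12 years. Infants are eligible; how many would enrol is unknown.

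The flat tier itself survives all of this.

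**Conclusion.** The point holds as a weakness in the sampling schedule. A site that follows the protocol exactly takes 7 mL per draw from any infant, however small. At 3 kg that is about 4.2 times as much per kg as the 20 kg child gives: 7 mL/kg over Days 0-2, 9.3 mL/kg over Days 0-3 and at most 14 mL/kg by Day 14.

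The infant weight is assumed; between 2.5 and 4 kg the ratio runs from 5.1 to 3.2. The absence of a limit is established only for the reviewed text. A limit held elsewhere would reduce the concern, but footnote 2 and Section IV.F would still need to point to it. This is a safety cost that is cheap to avoid. It is neither a demonstrated breach nor a threat to the primary analysis.

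**What to change.** In Table 1 footnote 2 and Section IV.F:

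1. Replace the single tier under 20 kg with a weight-scaled limit on research blood, per draw and cumulative, or cite the place where such a limit already stands. Count safety and anti-Xa samples taken for research towards it.
2. When the allowed volume is short, take the D-dimer sample for Aim 3a before material for banking.
3. State in Section IV.J.4 that an omission made because of the volume limit is not a deviation.
4. Add Day 0 to the Section IV.F narrative so that it agrees with Table 1 and the Day 0 visit list.

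One possible reference is the protocol's own 0.55 mL/kg at 20 kg. Applied to the research specimen alone, it changes draws only below about 12.7 kg. Once other research-obtained samples count, it would bind at higher weights too, by an amount that depends on volumes not stated.

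The cost is wording, fewer banked specimens and possibly fewer exploratory assays in the smallest children. At 0.55 mL/kg a 3 kg infant could give 3 × 0.55 = 1.65 mL per draw, and the 3 mL tube could not be filled below 3 / 0.55 = about 5.5 kg. A smaller tube would then be needed, or some D-dimer values could be lost. The primary bleeding endpoint does not depend on the research specimen. The dose endpoint needs only the anti-Xa samples, so the limit should leave room for them.

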#### 2. Inclusion Criteria

#### Inclusion Criteria for COVID-19 Infected Patients:

- 1. Children (birth to <18 years of age)
- 2. Positive nucleic acid test, antigen testing, or antibody testing for SARS-CoV-2 within the past 7 days
- 3. Hospitalized <72 hours post-admission
- 4. One or more signs and/or symptoms of COVID-19 illness within the past 72 hours, as follows:
  - i.) Cough
  - ii.) Fever (oral temperature >100.4°F/38°C)
  - iii.) Chest pain
  - iv.) Shortness of breath
  - v.) Myalgia
  - vi.) Acute unexplained loss of smell or taste
  - vii.) New/increased supplemental oxygen requirement
  - viii.) Acute respiratory failure requiring non-invasive or invasive ventilation
  - ix.) Encephalitis
- 5. Clinical suspicion that the above symptoms are related to COVID-19 infection and not an alternative etiology.

#### Inclusion Criteria for CMIS Patients Who Do Not Already Meet the Above Criteria for COVID-Infected Patients:

- 1. Children (birth to <18 years of age)
- 2. Signs and symptoms of COVID-19 Multi-System Inflammatory Syndrome (CMIS) including:
  - i.) fever ≥ 3 days;
  - ii.) Two or more of the following:
    - a) Rash of bilateral non-purulent conjunctivitis or muco-cutaneous inflammation (oral, hands, or feet),
    - b) Hypotension or shock,
    - c) Features of myocardial dysfunction, pericarditis, valvulitis, or coronary abnormalities (including ECHO findings or elevated troponin/NT-proBNP),
    - d) Evidence of coagulopathy (by PT, PTT, or d-Dimer)
    - e) Acute gastrointestinal problems (diarrhea, vomiting, abdominal pain)
  - iii.) Elevated markers of inflammation (erythrocyte sedimentation rate, C-reactive protein, or pro-calcitonin);
  - iv.) No other obvious microbial cause of inflammation, including bacterial sepsis, staphylococcal or streptococcal shock syndrome;
  - v.) Known exposure to a SARS-CoV-2 positive case, as documented by clinical history

# 3. Exclusion Criteria (for both COVID-19 and CMIS)

- 1) Patient's expected length of hospitalization is < 2 days
- 2) Receiving therapeutic dosing of anticoagulation (NOTE: pre-enrollment prophylactic enoxaparin administration is not an exclusion criterion)
- 3) Receiving ASA dosing > 5 mg/kg/day
- 4) Clinical-relevant bleeding (see criteria under Primary Outcome, below) within the past 72 hours
- 5) Platelet count <50,000/µL within the past 24 hours
- 6) Prothrombin time (PT) ≥2 seconds above the upper limit of age-appropriate local reference range within 24 hours prior to enrollment, unless PT was <2 seconds above upper limit within 24 hours prior to start of anticoagulation for routine clinical care OR unless a PT mixing study at either of these time points indicates the absence of a coagulation factor deficiency\*

- 7) Activated partial thromboplastin time (aPTT) ≥4 seconds above the upper limit of age-appropriate local reference range within 24 hours prior to enrollment, unless PTT was <4 seconds above upper limit within 24 hours prior to start of anticoagulation for routine clinical care OR unless a PTT mixing study at either of these time points indicates the absence of a coagulation factor deficiency\*

- 8) Fibrinogen level <75 mg/dL
- Severe renal impairment, as defined by estimated glomerular filtration rate (eGFR) <31 mL/min/1.73 m^2, as calculated by the Schwartz formula
- 10)Parent or legally authorized representative unwilling to provide informed consent for patient participation.

\*NOTE: A PT-based or PTT-based mixing study indicates the absence of a coagulation factor deficiency if the originally-prolonged clotting time in the assay does not correct to within the age-appropriate local reference range upon the addition of pooled normal plasma to patient plasma in a 1:1 ratio.

#### NOTE regarding pregnancy and eligibility:

A patient that is pregnant while enrolled in this study will remain eligible for this study.

#### F. Description and Justification of Procedures, Measures, and Data Collection Tools:

There will be minimal laboratory assays, examinations, or other procedures performed solely for the purposes of this study and not currently part of best/standard clinical care.

The first is an additional 11 mL blood specimen (7mL in participants <20kg) obtained at visits on post-enrollment days 1 and 2 (and days 3, 7, and 14 if still hospitalized) for protocol-specified research laboratory investigations (D-dimer, IL-6, anti-SARS-CoV-2 IgG/IgM, and CloFAL assay) and future unspecified research (i.e., banking of plasma, DNA isolated from the buffy coat, and isolated PBMCs). These biospecimens will be stored in the Johns Hopkins All Children's Pediatric Biorepository at the Clinical Coordinating Center. All biospecimen storage tubes are pre-labeled with a unique 2D

barcode, with the association between the barcode and the participant's unique study ID maintained in the Biorepository's secure, web-based, password-protected Lab Information Management System (LIMS) maintained behind the information technology firewall at Johns Hopkins All Children's Hospital. Biospecimens will be used to identify and validate putative prognostic biomarkers in pediatric venous thrombosis and COVID-19-related illness. The genetic investigations will involve candidate genes, a genomewide association study (GWAS), and whole genome sequencing approaches in deoxyribonucleic acid. The Johns Hopkins All Children's Pediatric Biorepository uses a secure database to store all data related to the samples, behind the institutional firewall. Following completion of the protocol-specified aims, external requests for specimens in the COVAC-TP trial biobank will be vetted and made available through the National Institutes of Health (NIH), in accordance with NIH policies on data and biospecimen sharing. The second procedure will be obtaining a contrast enhanced computed tomography scan of the chest within 24 hours preceding discharge from the hospital (if not already obtained clinically during hospitalization) to assess for pulmonary emboli. Throughout their study participation, up to and including visit 6, patients will be assessed for bleeding and VTE events by their inpatient medical provider team with any SAEs being documented in the case report forms (supported by source documentation in the patient's electronic medical record) and reported to the Medical Safety Officer (MSO) as described in Section J.2. The MSO will perform an independent determination of each SAE that has been locally determined by the responsible site PI, regarding relatedness to study intervention. If EITHER determination is that the SAE is "related", the SAE will be reported to the DSMB chair. The DSMB will then assess whether any action is needed, depending on the nature of the SAE. Adverse events (and symptoms of concern for possible VTE or clinically-relevant bleeding) will be further assessed at a long-term follow up visit 30 days (+/- days) after enrollment via telephone call from a study team member.

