The Schedule of Assessments is shown in Table 1. SAE monitoring and safety laboratory monitoring occurs on days 1-3, and on days 7 and 14 if the patient is still hospitalized. For all participants, pertinent clinical data will be captured as follows: results of coagulation and thrombophilia testing; nature of any major or clinically-relevant non-major bleeding episodes (as defined in Section IV B, above) during the anticoagulant therapy period (with detail as to amount of any related blood transfusion and/or any other intervention required—see also Data and Safety Monitoring Plan section); and nature of any new onset VTE (with detail as to signs/symptoms and anatomic site). PDFs of the REDCap electronic case report forms (eCRFs), as well as SAE report forms, are provided in the Manual of Operations. All SAEs and enoxaparin regimen adherence will be tracked

throughout hospitalization, and SAEs will continue to be tracked through 30 days postenrollment.

Children will complete their participation in the trial at the 30 days (+/- 2 days) postenrollment end-of-study telephone visit. As noted previously, the primary safety endpoint collection also occurs at the 30 days (+/- 2 days).

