1. STUDY OBJECTIVES

1.1. SPECIFIC AIM 1

- To investigate the safety of in-hospital thromboprophylaxis with twice-daily low-dose enoxaparin thromboprophylaxis (starting dose, 0.5 m/gkg subcutaneously q12 hours, adjusted to achieve a 4 hour post-dose anti-factor Xa level of 0.20-0.49 anti-Xa U/mL) in children hospitalized with COVID-19 related-illnesses, as measured by the cumulative incidence of ISTH-defined [10] clinically-relevant bleeding (primary endpoint).

1.2. SPECIFIC AIM 2

- To determine the median twice-daily enoxaparin dose, as measured in mg/kg, required to achieve a 4 hour post-dose anti-factor Xa level of 0.20-0.49 anti-Xa U/mL in children hospitalized with COVID-19 related-illnesses, and to compare dose-requirements by age group (birth to <1 year old, 1-<6 years old, 6-<13 years old, and 13-<18 years old).

1.3. SPECIFIC AIM 3

- To investigate, on an exploratory basis, the efficacy of in-hospital thromboprophylaxis with twicedaily enoxaparin in children hospitalized with COVID-19, as measured by the proportion of serial D-dimer levels obtained at standardized time points that are <2 times the upper limit of normal (<2x ULN) values for age (Aim 3a; surrogate marker of efficacy), the cumulative incidence of radiologically-confirmed HA-VTE (Aim 3b; clinical efficacy), and the median duration of in-hospital increased respiratory support (new requirement for high-flow nasal cannula, non-invasive ventilation, and/or mechanical ventilation, relative to any at-home baseline requirement; Aims 3c, clinical efficacy).

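### A contrast chest CT done before the first study dose waives the pre-discharge CT, so Aim 3b looks unevenly for clinically unsuspected emboli arising on prophylaxis.

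*Protocol*

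**What the plan says.** The scan is described once, in Protocol IV.F: "The second procedure will be obtaining a contrast enhanced computed tomography scan of the chest", to be done "within 24 hours preceding discharge from the hospital (if not already obtained clinically during hospitalization) to assess for pulmonary emboli". It does not appear in Table 1, in the day-by-day visit lists or in the SAP. Table 1 instead bases VTE detection on symptoms and examination: "VTE event (based on focused interim H&P, with radiological confirmation when suspected clinically", marked from Day 1 to Day 30.

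The timing of entry comes from the inclusion criterion "Hospitalized <72 hours post-admission" and from the screening column of Table 1, which uses the same 72-hour window. The exclusions include "Receiving therapeutic dosing of anticoagulation (NOTE: pre-enrollment prophylactic enoxaparin administration is not an exclusion criterion". No exclusion names existing VTE.

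The SAP (section 1.3) states the endpoint as "the cumulative incidence of radiologically-confirmed HA-VTE (Aim 3b; clinical efficacy". SAP 3.3 (Exploratory Outcomes) and 4.4 add that it will be a cumulative incidence with a 90% interval. They give no start point, no rule on the date of the CT, and no rule for a child with no scan after dosing. SAP 4.1.4 specifies complete-case analysis without saying whether such a child is event-free or missing.

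**The concern.** A scan taken before the first study dose cannot show an embolus that arises on prophylaxis. Under the waiver as worded, that scan still removes the pre-discharge CT. The same endpoint is then pursued at two intensities. Some children get systematic imaging near the end of exposure. Others get imaging only when a clinician suspects VTE. Which group a child falls into depends on whether the clinical team ordered an early contrast CT. That choice may track respiratory severity, although the documents do not say so.

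The trial has a single arm, so uneven ascertainment cannot cancel against a control group. Aim 3b is labelled clinical efficacy, and among 38 children one event moves the estimate by 1/38 = 2.6 percentage points. Under the present plan, a reader of the result could not tell how many of the 38 were imaged for emboli after prophylaxis began.

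**Working it through.** **Step 1: can a pre-dose scan meet the waiver?** IV.F accepts a scan obtained clinically during the hospitalization. Enrolment can follow admission by up to 72 hours, and study enoxaparin follows enrolment. A contrast CT done on arrival is therefore within the hospitalization and before the first study dose. It meets the waiver as written.

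**Step 2: does anything restore imaging for that child?** Table 1 and the visit lists provide VTE assessment on Days 1, 2 and 30, and on Days 3, 7 and 14 if the child is still in hospital, with imaging on suspicion. This finds suspected VTE in every child. It does not look for unsuspected emboli in children whose discharge scan was waived. The SAP makes no adjustment to the denominator.

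**Step 3: size.** The plan gives no figure for this point, so there is none to reproduce for Aim 3b. Two inputs are assumptions, shown as ranges:

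- f, the share of children whose only contrast CT predates the first dose: 10% to 50%.
- p, the rate of clinically unsuspected emboli arising on prophylaxis: 2% to 10%.

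If p is the same in both groups, the detected rate of unsuspected emboli in all dosed children is p × (1 − f), and the expected number missed is 38 × p × f.

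| p | f | Detected rate | Expected missed among 38 |
|---|---|---|---|
| 2% | 10% | 0.02 × 0.90 = 1.8% | 0.08 |
| 5% | 10% | 0.05 × 0.90 = 4.5% | 0.19 |
| 5% | 25% | 0.05 × 0.75 = 3.75% | 0.48 |
| 5% | 50% | 0.05 × 0.50 = 2.5% | 0.95 |
| 10% | 50% | 0.10 × 0.50 = 5.0% | 1.9 |

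The relative loss equals f whatever p is. It applies to the unsuspected component only, since suspected VTE is sought in everyone.

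**Step 4: precision of the imaged subset.** The subset has 38 × (1 − f) children. With no events, the upper limit of an exact 90% interval is 1 − 0.05^(1/n). At n = 38 this is 7.6%, which matches the limit the plan quotes for 0/38 on the bleeding endpoint. At f = 10% (n = 34) it is 8.4%. At f = 25% (n = 28 or 29) it is 10.1% or 9.8%. At f = 50% (n = 19) it is 14.6%.

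**The case against.** The strongest reply is that the effect is small and the endpoint exploratory. Even the largest assumed inputs lose about two children, and the exact 90% interval for 1/38 already runs from 0.1% to 11.9%. Aim 3b has no threshold, comparator or decision rule. Not repeating a contrast CT in a child is also a defensible choice. All of this stands and sets the severity. It does not remove the case for reporting who was scanned and when, which costs almost nothing.

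A second reply is that the scan may not be operative at all, since it is in neither Table 1 nor the visit lists. That is a genuine contradiction and has to be settled first. If imaging was done only on suspicion, the waiver has nothing to replace.

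A reader might also infer three stronger things that the documents do not support:

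- That any clinical chest CT triggers the waiver. The procedure is a contrast-enhanced scan to look for pulmonary emboli, so a non-contrast CT is not naturally covered.
- That emboli in general are missed. Only clinically unsuspected ones are.
- That emboli predating treatment are counted as failures of prophylaxis. No text directs this, and several points weigh against it: the captured item is the "nature of any new onset VTE (with detail as to signs/symptoms and anatomic site", VTE checks start on Day 1, children on therapeutic anticoagulation are excluded, and VTE is centrally adjudicated under a charter not supplied here. The wording leaves it open, because neither the word new nor the endpoint has a time origin, but it cannot be asserted.

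A silent embolus already present at enrolment and first seen on the discharge CT is a different problem. It comes from having no baseline imaging and would exist under any wording of the waiver.

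**Conclusion.** The point holds in a limited form. Following IV.F exactly, children with a pre-dose contrast CT have no scheduled imaging after prophylaxis starts, while the others are screened at discharge. The all-dosed Aim 3b figure therefore understates unsuspected emboli arising on prophylaxis by roughly the share of children with only a pre-dose CT. At an assumed 5% silent rate, shares of 10% to 50% turn 5% into 4.5% to 2.5%.

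This rests on the discharge CT having been carried out as IV.F describes, on an equal silent rate in both groups, and on inputs that are not in the documents. If children scanned early carry a higher risk, the loss is larger than f; if lower, it is smaller. The absolute effect lies well within sampling error. Primary safety, the sample size of 38 and the pause boundaries are untouched. Minor: a cheap improvement.

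**What to change.** SAP 2.5 records enrolment as complete at 38, so this is a change to analysis and reporting, with no added scans.

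1. In SAP 3.3 (Exploratory Outcomes) and 4.4, define Aim 3b as VTE first shown on imaging after the first study dose. List VTE seen on a pre-dose CT separately as a baseline finding. Because prophylactic enoxaparin before enrolment is allowed, flag children who received it, since for them a pre-dose scan is not always a scan before any prophylaxis.
2. Report the embolus proportion among children with a contrast chest CT after the first dose beside the all-dosed figure, with both denominators and exact 90% intervals. Add the time from first dose to CT, because a clinical scan soon after dosing also meets the waiver and is not end-of-exposure imaging.
3. Show VTE found on suspicion separately from VTE found by screening.
4. State as a limitation that, without baseline imaging, a silent embolus present at enrolment cannot be told apart from an incident one. The definition in item 1 does not solve this.
5. Reconcile Protocol IV.F with Table 1 and the visit lists on whether the pre-discharge CT was part of the study, and report how many children had it.

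The cost is a few sentences in the SAP, plus the CT dates set against first-dose dates, which should be obtainable from the medical and dosing records. The downside is a smaller denominator and wider intervals for the imaged subset.
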